**2. ADEQUACY OF PROTECTION AGAINST RISKS****Recruitment and Informed Consent Procedures:**

We will recruit at least 40 overweight, middle aged, nondiabetic subjects and 45 subjects with Type 2 diabetes by local advertising. Consent will be initially obtained during telephone screening performed by a research fellow or the study coordinator. Formal consent procedures which adhere to the Committee on Clinical Investigations of the Albert Einstein College of Medicine will be followed. Specifically, each subject will be verbally informed in layman's language of the purpose, benefits and possible risks of the studies. They will then read the written consent form in the presence of a member of the research team and a physician who will answer any further questions. The subject and

witness shall be asked to sign the consent form which will be kept in the patient's chart. Each subject's potential participation in related experiments (for example, when each subject is asked to perform repeat studies) will be explicitly stated.

All clinical data on the subjects will be confidential. Data generated in these studies will be considered only relevant for research purposes and will not be included in any clinical databases or the patient's chart. Since the GCRC databases are coded, the study data will not be available on any clinical database system.

### **Protection Against Risk:**

#### **Procedures employed to protect subjects from undue risks include the following:**

- 1) Blood withdrawal: Blood withdrawal during any single study will be limited to less than 190cc and subsequent studies will be separated by at least, a four week interval. The infusion and withdrawal catheters may produce infection or local hematoma, but strict aseptic technique will be observed by the experienced physician performing the procedure.
- 2) 20% glucose: Vein irritation with 20% glucose infusion will be prevented by use of a large-bore antecubital vein.
- 3) Glucagon: Symptoms of mild nausea will be treated with antiemetic medications, if needed.
- 4) Hypoglycemia: All of these studies will be performed by a physician, hypoglycemia will be prevented by blood glucose sampling every 5-10 minutes and if inadvertent hypoglycemia develops can be rapidly treated by glucose infusion.
- 5) Resveratrol: Given data from a number of *in vitro* studies demonstrating that resveratrol can be an inhibitor of various cytochrome P450 enzymes involved in drug metabolism, use of the following drugs will be exclusionary for this study: anti-epileptics, mexilitene, quinidine, cyclorpsorine, tacrolimus, HIV protease inhibitors. Dosages of up to 1000 mg/day have been widely used without reports of adverse effects.

### **3. POTENTIAL BENEFITS OF THE PROPOSED RESEARCH TO THE SUBJECTS AND OTHERS**

The study will be of no direct benefit to the subject, although subjects may gain a better understanding of their own metabolic processes. The results of the study will contribute to generalizable knowledge about the effects of resveratrol on insulin action, mitochondrial function, muscle strength and neurocognitive function.

### **4. IMPORTANCE OF THE KNOWLEDGE TO BE GAINED (Risk: Benefit Ratio):**

The risks involved are minimal as all procedures are well established. The study may result in a better understanding of the role of resveratrol in determining insulin action in humans. As described above, a number of mechanisms exist to ensure safety of subjects. All studies will be performed by a physician and nurse in attendance in the CRC procedure unit with emergency equipment readily accessible. The PI, coinvestigators, and research team have a combined experience of over 10 years in human investigation, and sufficient care in choice of subjects should minimize the risks. The scientific value of these studies is to develop an understanding of the mechanism of an important clinical and potentially-exciting device for the treatment of diabetes.

### **INCLUSION OF WOMEN**

As mentioned in the human subject characteristics section above, the study will exclude pregnant women because of the use of radioactive tracer. Otherwise, an anticipated 50% of subjects will be female based on preliminary data and the population distribution in the Bronx.

**INCLUSION OF MINORITIES**

We anticipate that 50% of our study subjects will be from minority communities, based on our preliminary data and the population distribution in the Bronx. Recruitment strategies to encourage minority enrollment include advertisements in ethnic newspapers and magazines.

**INCLUSION OF CHILDREN**

The purpose of this study is to determine effects of resveratrol on age-related parameters in middle-aged subjects and in those with Type 2 diabetes and hence no children will be studied.

**DATA SAFETY AND MONITORING PLAN (DSMP):**

All human subject research being conducted at the Einstein GCRC must have a DSMP. The guidelines for Data and Safety Monitoring have been established by the GCRC Research Subject Advocate (RSA), and approved by the Assistant Dean for Compliance who oversees human research subject safety at the Albert Einstein College of Medicine.  
<http://gcrcweb.aecom.yu.edu/gcrc/dsm.htm>

**Adverse Event Monitoring:**

Process: Data and safety monitoring for this study will be performed by the principal investigator on an ongoing basis. All volunteers will be seen by the P.I. or her research staff. Laboratory data will be reviewed by the P.I. within 24 hours of receipt.

Reporting: All adverse events will be compiled, and reported in summary form, on an annual basis to the IRB, and at the conclusion of the study. Unanticipated (non-serious) adverse events will be reported to the IRB within 30 days and serious adverse events will be reported to the IRB within 48 hours by phone, email or fax

**Recruitment Monitoring:**

Process: The P.I. will assess the recruitment and retention of study subjects on an ongoing basis. The recruitment goal for this protocol is 40 subjects to complete all of the proposed studies.

Reporting: Summary statistics regarding recruitment and retention of study subjects will be reported to the IRB on an annual basis, and at the conclusion of the study.

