### **EXPERIMENTAL APPROACH AND METHODS:**

#### **STUDY POPULATION AND RECRUITMENT**

Overweight, middle aged and type 2 diabetes subjects will be recruited by a variety of approaches, as described below. Subjects will range in age from 21 to 65 years, will be overweight (BMI 25-30 kg/m^2) with and without diabetes mellitus. All subjects with a history of liver disease or liver abnormalities, hyperlipidemia, hypertension, heart disease, cerebrovascular disease, seizures, bleeding disorders, muscle disease, a known history of ovarian, uterine, breast cancer or smoking will be excluded. The following subjects will also be specifically excluded: mentally disabled persons, prisoners, pregnant women, subjects with a history of ethanol or drug or toxin exposure which could be associated with neuropathy, any subject deemed incapable of giving voluntary informed consent, and subjects with a history of a bleeding disorder or with a prolonged PT or PTT. Furthermore, subjects allergic to Novocain, Benzocaine and Lidocaine will also be excluded. Given potential concerns (based on *in vitro* observations) that resveratrol might inhibit various cytochrome P450 enzymes involved in drug metabolism, use of the following drugs will be exclusionary for this study: anti-coagulant and anti-platelet drugs, anti-epileptics, mexilitene, quinidine, cyclosporine, tacrolimus, and HIV protease inhibitors (see below under Protection of Human Subjects). NSAIDS should be avoided as far as possible during the study period. Additionally, given confounding effects of extreme exercise on muscle triglyceride content, highly trained or professional athletes will be excluded from the studies.

Women in the child-bearing age-group will be allowed to participate in the studies provided that they have negative pregnancy tests within a week of the studies and that they are not breast-feeding. Children below the age of 18 will be excluded from the current protocol, given the use of labeled isotopes. Prior to their enrollment in the study the purpose, nature, risks and benefits of the study will be explained to all subjects and their voluntary, informed, written consent will be obtained. All subjects will have a screening visit to allow for clinical evaluation, including history, physical examination and consent procedures.

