### **General Experimental Conditions:**

On the day of the first pancreatic clamp study the patients will receive a 28 days" supply of resveratrol capsules. The pilot study will be an open-labeled study. The study design requires that all 55 subjects participate in all of the proposed studies, as outlined below. Consequently, additional subjects will be recruited to compensate for those subjects who cannot complete all of the required studies.

Prior to each study, subjects will meet with study personnel to discuss dietary recommendations. Each subject will be instructed to follow a standardized diet plan for three days prior to each of the clamp studies (40% fat: 20% saturated, 10% polyunsaturated, 10% monounsaturated; 35% carbohydrate; 25% protein). Subjects will be asked to refrain from vigorous exercise for three days prior to each clamp study.

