### **Aim 1: To study the effects of resveratrol on age-related insulin resistance**

*We hypothesize that treatment of overweight, middle aged or Type 2 diabetes subjects with resveratrol will result in improved insulin sensitivity, as demonstrated by increased insulin-stimulated glucose uptake and enhanced insulin-mediated suppression of glucose production.*

We will study the following subject group:

- **Overweight and either young or middle aged** (BMI 25-30 kg/m^2, age 21-65) nondiabetic subjects, n=40 diabetic subjects (BMI=25-35) n=15

Each subject will receive a 28 day course of **resveratrol** (n=55). RevGenetics will supply the resveratrol (500 mg capsules; 2 capsules bid) for our proposed studies. A certificate of analysis has been provided by the manufacturer.

A comprehensive study of whole-body insulin action will be undertaken with specially designed „stepped” euglycemic (~90 mg/dl) -hyperinsulinemic clamp studies, both before and after administration of resveratrol.

Thus, we will compare the following parameters under paired conditions in each subject, on day 0 and day 28 of resveratrol treatment:

- a. **hepatic insulin action:** this will be determined as the ability of low infusion rates of insulin (20 mU/m^2.min above basal requirements) to suppress glucose production during the “**low insulin phase**” of the clamp studies.
- b. **peripheral insulin action:** this will be determined as the ability of high infusion rates of insulin (80 mU/m^2.min above basal requirements) to stimulate glucose uptake during the “**high insulin phase**” of the clamp studies.

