##### **Human Subject Characteristics**

The study population will consist of at least 40 nondiabetic subjects and 15 diabetic subjects with the following characteristics: ages 21-65 years, with BMI between 25 and 30 kg/m^2. The following subjects will be specifically excluded: children, mentally disabled persons, prisoners, pregnant women, fetuses, subjects with a history of ethanol or drug or toxin exposure which could be associated with neuropathy, any subject deemed incapable of giving voluntary informed consent, and subjects with a history of a bleeding disorder or with a prolonged PT or PTT; a history of uterine, breast, or ovarian cancer, renal disease, and liver disease or impairment. Women in the child-bearing age-group will be allowed to participate, provided they have negative pregnancy tests. The research topic to be studied is not relevant to the involvement of special classes or groups of subjects and therefore no criteria for their involvement are specified.

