**Table II TARGETED/PLANNED ENROLLMENT: Number of Subjects**

ETHNIC CATEGORIES	Sex/Gender		
	Females	Males	Total
Hispanic or Latino	8	8	16
Not Hispanic or Latino	12	12	24
Ethnic Category: Total of All Subjects	20	20	40
RACIAL CATEGORIES			
American Indian/Alaska Native	0	0	0
Asian	0	0	0
Native Hawaiian or Other Pacific Islander	0	0	0
Black or African American	8	8	16
White	12	12	24
Racial Categories: Total of All Subjects	20	20	40

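### The protocol gives conflicting subject numbers (55 or 40 completers, 15 or 45 diabetic subjects, 25 or 55 for Aims 3 and 4) and two BMI ceilings for diabetic subjects (30 or 35)

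*Combined protocol and SAP*

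**What the plan says.** **Total.** General Experimental Conditions: "The study design requires that all 55 subjects participate in all of the proposed studies", and "additional subjects will be recruited to compensate for those subjects who cannot complete all of the required studies". Aim 1 defines the cohort as "nondiabetic subjects, n=40 diabetic subjects (BMI=25-35) n=15" and puts 55 on treatment. Human Subject Characteristics has "at least 40 nondiabetic subjects and 15 diabetic subjects with the following characteristics: ages 21-65 years, with BMI between 25 and 30". Recruitment Monitoring, by contrast, says "The recruitment goal for this protocol is 40 subjects to complete all of the proposed studies", and Table II ("TARGETED/PLANNED ENROLLMENT: Number of Subjects") totals 40 under a row covering all subjects.

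**Diabetic subjects.** Aim 1 and Human Subject Characteristics give 15. Recruitment and Informed Consent Procedures gives 45, beside a nondiabetic minimum of 40.

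**Aims 3 and 4.** Aim 3 first refers to 25 subjects aged 45-65, then lists assessments after treatment of 55. Aim 4 gives 25 in both places. Aim 2 applies the same 45-65 age label to all 55. The Schedule of proposed clinical studies books motor and cognitive testing on days -1 and 27 for subjects generally, including those with diabetes, and names no subset.

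**BMI of diabetic subjects.** Study Population and Recruitment: "Subjects will range in age from 21 to 65 years, will be overweight (BMI 25-30", applied to people "with and without diabetes mellitus". Human Subject Characteristics also stops at 30. Aim 1 goes to 35.

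**The concern.** Sample size and eligibility limits are figures that site staff, the IRB and the analyst all act on, and here they depend on which section is read. The Statistical Analysis section contains no sample-size calculation, so nothing else in the document settles which number is meant.

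Three things are at stake:

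- **Recruitment.** Progress is reported to the IRB each year, and the goal stated beside that duty is 40. Against that goal, recruitment could count as met before the 55-subject design is complete, possibly without diabetic subjects.
- **Aims 3 and 4.** Without a fixed denominator, nobody can tell later whether absent motor or cognitive results are missing data or planned subsetting.
- **Eligibility.** A diabetic subject with a BMI above 30 and up to 35 may enrol under one section and not under two others.

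**Working it through.** The figures as they stand in the current text:

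| Item | Figure | Section |
|---|---|---|
| Completers, whole study | 55 | General Experimental Conditions |
| Completers, whole study | 40 | Recruitment Monitoring |
| All subjects | 40 | Table II |
| Nondiabetic + diabetic | 40 + 15 | Aim 1; Human Subject Characteristics (40 as a minimum) |
| Nondiabetic + diabetic | 40 (minimum) + 45 | Recruitment and Informed Consent Procedures |
| Aim 2 | 55 | Aim 2 |
| Aim 3 | 25, then 55 | Aim 3 |
| Aim 4 | 25, twice | Aim 4 |
| BMI ceiling, diabetic | 35 | Aim 1 |
| BMI ceiling, diabetic | 30 | Study Population and Recruitment; Human Subject Characteristics |

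**Step 1: reproduce the plan's total.** 40 + 15 = 55. This matches General Experimental Conditions and the number treated in Aim 1.

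**Step 2: compare with the other total.** Table II adds up correctly: ethnicity 16 + 24 = 40, race 16 + 24 = 40, sex 20 + 20 = 40. The gap is 55 - 40 = 15, and 15/55 = 27.3%. Both 55 and 40 count people who complete every study, so enrolled versus completed does not explain the difference.

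**Step 3: the diabetic group.** 45 - 15 = 30. The recruitment section implies at least 40 + 45 = 85, which is 85 - 55 = 30 more than the design.

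**Step 4: Aims 3 and 4.** 55 - 25 = 30, and 30/55 = 54.5%.

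**Step 5: can an age split rescue the 25?** If 25 were the subjects aged 45-65, the other 55 - 25 = 30 would be aged 21-44, and Aim 3 would make sense. Three things prevent treating this as settled. Aim 1 defines no such subgroup. Aim 2 gives the 45-65 label to all 55, although the cohort runs from 21 to 65. Aim 4 gives 25 as the number treated.

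**Step 6: what the choice means for precision (illustration only).** The document states no alpha or power. Assuming a paired t-test, two-sided alpha 0.05 and 80% power, the detectable paired difference from the noncentral t distribution is 0.58 SD at n = 25, 0.45 SD at n = 40 and 0.39 SD at n = 55. At 90% power the values are 0.68, 0.53 and 0.45 SD.

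**The case against.** The best defence is that these are leftovers in an open-label pilot and change little.

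- **The 40 is probably the nondiabetic group, not updated when diabetic subjects were added.** This is plausible. But Recruitment Monitoring sets its goal for the whole protocol, and the Table II total row covers all subjects, so the conflict remains in the text.
- **45 counts people recruited, while 15 counts people completing.** The plan does expect replacements, so this conflict is less certain than the others. Still, no allowance is stated, and the nondiabetic minimum beside it is not inflated at all. The 45 remains unexplained.
- **Aim 4 is consistent with itself.** That is correct. Its conflict is with the rule that all 55 do all studies, and that sentence goes on to refer to the details that follow it. The contradiction inside Aim 3 is the sharper one.
- **Nothing closes recruitment at 40, and the 15 diabetic subjects are called for elsewhere.** This stands. Early closure is a possibility only.
- **The 55 has no clear majority behind it.** For the study total, four sections support 55 (General Experimental Conditions, Aim 1, Aim 2, Human Subject Characteristics) and two support 40 (Table II, Recruitment Monitoring). The 25 in Aim 4 is not a study total. It is fair to add that the nondiabetic 40 is a minimum in some places, so the exact split comes from Aim 1 alone.
- **No sum is wrong.** This is also true. The fault is inconsistency between sections, and the BMI conflict is a separate eligibility matter.

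**Conclusion.** The concern holds. The sections disagree in the current text, and no amendment log, redaction or damaged table accounts for it. The sizes are 40 versus 55 completers, 15 versus 45 diabetic subjects, 25 versus 55 for Aims 3 and 4, and a BMI ceiling of 30 versus 35 for diabetic subjects.

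The weight is moderate. The principal endpoint sits in Aim 1, which is consistent at 55, and there is no power calculation for the other numbers to invalidate. This should be corrected, but it does not undermine the main analysis. The conclusion rests on the stated figures alone; the detectable differences are illustrations and do not support it. The document does not establish which number or BMI limit was intended.

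**What to change.** 1. The investigators confirm one completer target by diabetes status and use it in General Experimental Conditions, Aim 1, Human Subject Characteristics, Table II, Recruitment and Informed Consent Procedures, and Recruitment Monitoring.
2. Unless they confirm another figure, Recruitment Monitoring and Table II change from 40 to 55 (40 + 15). The 45 diabetic subjects become 15, or are labelled as a recruitment or screening allowance.
3. State whether Aims 3 and 4 use all 55 or a defined subset of 25 with its selection rule, and make both aims and the schedule agree.
4. Clarify what the 45-65 age label means in Aims 2 to 4, and remove it where the whole cohort is meant.
5. The investigators reconcile the diabetic BMI limits in Study Population and Recruitment, Aim 1 and Human Subject Characteristics.

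**Cost.** If 55 is confirmed, this is a text amendment with no added subjects. Table II needs more than a new total: the 15 diabetic subjects must be allocated by sex, ethnicity and race. An odd total can only approximate the equal sex split anticipated under Inclusion of Women (27/55 = 49.1% or 28/55 = 50.9%), which is harmless because that split is an expectation, not a quota. If 45 diabetic subjects are confirmed, that is 30 more than Aim 1 plans and is a change to the study, not only to its wording.

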**Early Study Termination:**

Process: The P.I. will determine if the study is to be terminated prior the scheduled study conclusion. Early study termination will be considered in the event of an unanticipated serious adverse event determined to be possibly, probably or definitely related to the study. The P.I. may also terminate the study if a positive drug screening test at any time during the study is found. Payment will be reduced to \$50 and the subject will be withdrawn from the study

Reporting: The P.I. will report the decision to terminate the study to the IRB within 48 hours of this determination. The P.I. will submit a narrative description of the reasons for early termination of the study within 10 days.

**DATA SHARING**

We respect that the rights and privacy of people who participate in NIH-sponsored research must be protected at all times. Thus, data intended for broader use will be free of identifiers that would permit

linkages to individual research participants. We and our collaborators will make the data and associated documentation available to users only if they provide: (1) a commitment to using the data only for research purposes and not to identify any individual participant; (2) a commitment to securing the data using appropriate computer technology; and (3) a commitment to destroying or returning the data after analyses are completed. We expect that the results of this study will be presented at national scientific meetings and published in peer reviewed journals.

